The PI will review reports reflecting data quality, safety, and monitor for potential adverse events and protocol adherence. The project coordinator, study staffs will meet with the PI weekly to review the progress of the study. The members of the investigative team and scientific advisors will meet monthly to support the study. A Safety Monitoring Committee (SMC) will be formed, consisting of Johns Hopkins University clinician faculty members who are independent of this proposed feasibility study. The SMC will be responsible for overall monitoring of the safety of participants in this proposed study and overseeing the PI, Co-Is, and research assistant.

The PI will be responsible for managing all data, securing privacy and confidentiality, minimizing and identifying risks, monitoring and reporting adverse events or any safety issues, and complying with timely reporting requirements to all applicable regulatory bodies for any adverse events or unexpected problems. Monthly reports will be completed by the PI detailing participant demographics, recruitment status, treatment retention rates, protocol compliance, data gathered and accuracy, and quality assurance or regulatory issues that transpired, and summary of any adverse events. The research team (PI, Co-Is, and research assistant) will meet weekly via face to face or conference calling to discuss data and safety monitoring.

The SMC will meet annually (or more frequently if needed) and review the annual reports completed by the PI; review study safety, integrity, and progress including any adverse events; provide advice in relation to continuing, changing, or terminating the study when necessary; require more frequent reporting as needed; audit the study for compliance and verify authenticity of data; and assess that the research team is complying with informed consenting and other required regulations. These annual meetings will be conducted face-to-face or through conference calls.

Date: November 14, 2018

Principal Investigator: [name]

Application Number: IRB00175781

The PI, in consultation with the SMC, will provide reports at intervals as required by National Institute of Health and/or other regulatory bodies as well as provide immediate reports as required regarding any adverse or unanticipated problems that may occur.

Phase 2: Pilot testing the adjusted iHBE program

4. Study Procedures

Design: Randomized waiting list controlled trial design

Phase 2 Specific Aims

Aim 2: Pilot testing the effect of the tailored iHBE on fatigue, pain, affective well-being, resilience and BDNF level among low-income cancer survivors living with co-morbid conditions at completion (12 weeks) and 6 months in comparison to usual care waiting list group.

After adjustment in the protocol based on Aim 1, 50 participants who meet the inclusion criteria will be randomly assigned to a 12-week experimental (preferred physical activities) group or a usual care usual care (waiting list) group. Variables will be measured at baseline, completion (12 weeks) and 6 months.

Hypothesis 2: After controlling for the age, gender, race, and BMI, participants in the experimental group will have a greater decline in fatigue, pain, and a greater increase in AWB, resilience and BDNF level from baseline to program completion and 3 months compared to the usual care group.

Aim 3: Examine the association between the changes in the biomarker (BDNF) in serum and sweat after the 12-weeks from baseline and at 3 months post program completion from baseline iBHE program. Hypothesis 3: the change in the serum BDNF level is positively associated with a change in the sweat BDNF level at the after the 12-weeks from baseline and at 6 months from baseline iBHE program.

Sample and Setting:

The study participants will be recruited from the home health care agencies in Baltimore, Maryland, Johns Hopkins Comprehensive Cancer Center and Johns Hopkins Hospital.

Inclusion criteria are (1) participants diagnosed with solid tumor cancer who have completed cancer treatment at least 6 months; (2) diagnosed with diabetes and/or hypertension for at least a year; (3) aged 21 years or older, (4) have an annual household incomes of below \$30,000 for families of three, (5) the average fatigue level within the past 7 days at the level of 3 or more on the 0 (no fatigue) to 10 (worse fatigue) Likert scale and (6) give informed consent.

Exclusion criteria are those (1) currently undergoing treatment for cancer; (2) have an active infection (e.g., fever, localized redness, swelling, sinus congestion); and/or (3) diagnosed with a psychological disorder (e.g., suicidal or homicidal tendencies, extreme anxiety or depression).

Sample size justification

Phase 2: With an alpha level of .05, the statistical power of 0.80, and 25 participants per group, we will be able to detect significant differences of moderate to large effect sizes of 0.65 when comparing change across baseline, 3-months, and 6-months between the two groups. With an attrition rate of 12% (22 participants per group), the detectable effect size increases to 0.69. Since this is a pilot study and not powered to detect small to moderate effect sizes, we will pay close attention to the effect size, rather than statistical significance. These effect size estimates will be used to inform future research trials.

Date: November 14, 2018

Principal Investigator: [name]

Application Number: IRB00175781

Randomization: Eligible participants will be randomized in a 1:1 allocation ratio to one of the two treatment arms. The electronic Research Electronic Data Capture (REDCap), a randomization application will be used to randomly assigned the participants to the groups

Data Collection Schedule and Procedures. Upon receiving approval from the Johns Hopkins University Institutional Review Board, the study flyer will be posted and distributed at the home health care agencies in Baltimore, Maryland, Johns Hopkins Comprehensive Cancer Center and Johns Hopkins Hospital.

Recruitment, Informed Consent, and Confidentiality. Recruitment methods for this study include (1) distributing and posting flyers, with a tear-off phone number to speak with the principal investigator (PI) as necessary, posted at the hospital (2) face-to-face recruitment for potential participants during cancer support group meetings; and (3) word-of-mouth. Potential participants will receive a verbal explanation by phone or face to face meeting in terms suited to their comprehension of the purpose, procedures, and potential risks of the study. During the screening for eligibility process, an oncologist will be available for consultation. The oncologist will be notified and consulted for the appropriateness of the exercise for participants who self-report having co-morbidities. The participants and family or legal guardian will have an opportunity to carefully review the consent form and ask questions regarding this study prior to signing. Participants will be encouraged to consult with their primary doctor if any concern or an additional question. Participants will be informed that they may withdraw from the study at any time without prejudice to themselves.

Participants will be approached and screened for the annual income below \$30,000 for families of three, average fatigue level within the past 7 days at the level of 3 or more on the 0 (no fatigue) to 10 (worse fatigue) Likert scale, the self-report perceived ability to walk for six-minute and the exertion level after the walk on a 0-10 numeric perceived exertion scale (0 = no exertion at all to 10 = maximal exertion). Eligible participants will be asked if they would like to participate and to sign the informed consent. Participants will be asked to have the research team visit their home for the initial assessment and to provide instruction on the exercise, the physical activity tracker and how to complete the questionnaire via the phone application for 4 weeks, followed by phone follow up for 7 weeks. Participants will be asked to wear the FitBit Charge 2 on the non-dominant arm and respond to the phone application daily for 12 weeks. Participants' peripheral blood will be drawn at week 1 and week 12 by a registered nurse or certified phlebotomist. We will ask the participant to have a sweat pad placed on their upper abdomen or flank for 72 hours to collect the sweat at baseline (before the program) and week 12 (at the program completion).

At the end of the program, a research team member will visit participants' home and evaluate the participants' perception and satisfaction for the program using a open ended questionnaires. Participants will be asked to complete the questionnaires. Participants' blood and sweat will be collected.

Intervention/Independent Variables

Tailored Technology-Enhance Home-based Exercise Program:

The tailored technology enhanced home-based exercise (iHBE) program: Participants in this group will receive an adjusted (based on the feedback from phase 1)12-week program with 1 assessment home visit session, 5 home visits during exercise and 7 follow up phone calls. The technologies, a wearable device and a smartphone application, will be used as a tool to monitor physical performance (heart rate, step count), provide immediate feedback, send daily reminding message through mEMA. The coded raw data without personal identification information from the wearable device will be sent to the servers where we can store it in the database alongside the mEMA data and create custom reports showing HR 30 minute before each EMA survey, showing HR and previous self-report responses before/ after each automatically triggered

Date: November 14, 2018

Principal Investigator: [name]

Application Number: IRB00175781

EMA.

Usual Care (Waiting List) Group: The usual care waiting list group will receive educational booklets about a healthy lifestyle and cancer survivorship. Participants will be asked to wear the wearable device during the waiting period to monitor the PA (steps and heart rate). They will receive a notification to rate their daily fatigue level for 3 months. Usual Care participants will receive the iHBE after the conclusion of the study (as described above).

Variables and measurements.

The study variables will be measured as follows:

Measure	Description	Psychometrics
NINR Common Data Elements (CDEs)	23-item; measure demographic and disease information data	
PROMIS Short Form V1.0-Fatigue 6a	6-items; self-reported fatigue (frequency, duration, intensity) and the impact to physical, mental, and social activities, has five response options (1 or never to 5 or always).	Initial psychometric properties have shown an internal consistency reliability coefficient of greater than 0.80. ⁵²
PROMIS Pain Intensity – Short Form 3a V1.0.	Universal and not disease-specific instrument for pain, 3-items (worst, average, and current pain) measure from 1 (no pain) to 5 (very severe).	Conceptually validated with established reliability Test-retest values = .83 to .93. (PROMIS, 2015)
Wrist worn wearable device: FitBit Charge 2	PA (steps count and Heart rate) tracking device (wrist worn)	Intraclass Correlation Coefficients with ActivPAL are 0.81 and 0.96 respectively, $p < .01$. (Kooiman et al., 2015)
Connor-Davidson Resilience Scale	10 item self-report rating scale 0 (not true at all) to 4 (true nearly all the time)	Good internal consistency (Cronbach's alpha 0.85) and constructs validity. (Campbell-Sills & Stein, 2007)
Short form survey (SF-36)	36 item self-report instrument measure 2 domains: physical well-being and affective well-being.	Good internal consistency for every scales (Cronbach's alpha ≥ 0.70). (Busija et al., 2011)

Serum and Sweat BDNF protein levels will be measured by the enzyme-linked immunosorbent assay (ELISA). Participants' peripheral blood will be drawn during home visits, the sweat patch will be placed on the participants' upper abdomen or flank for 72 hours to collect the sweat at baseline, 12 weeks and 3 months after the program completion. The ELISA will be performed according to manufacturer's guide by one laboratory technician.

Data Collection Schedule and Procedures:

Phase two is a pilot testing of the adjusted iHBE program effectiveness on the symptoms (fatigue and pain) affective well-being, resilience and BDNF level. A randomized usual care (waiting list) trial phase will be used. The study flyers will be posted at the home health care agencies, Johns Hopkins Comprehensive Cancer Center and Johns Hopkins Hospital. Eligible participants will be contacted by the principal investigator or research assistant who will explain the purpose of the study and requirements, and provided the study information and consent form. After providing the signed consent form, participants will complete the baseline assessment including the questionnaire, physical function (FTSST and 6MWT)

Date: November 14, 2018

Principal Investigator: [name]

Application Number: IRB00175781

and blood samples. A pre-installed application smartphone and a wrist-worn wearable device (FitBit Charge 2) will be loaned to the participants. The online account specific to the participant will be assigned using code. No personal information will be stored separately. Participants will be asked to wear the FitBit Charge 2 on the non-dominant arm and respond to the mEMA application to monitor their free-living PA level for 7 days then randomly assigned to the experiment and usual care waiting list group. Participants in the iHBE group will receive one assessment home visit, 5 home visits and 7 follow up phone calls during the iHBE program. Then a home follows up visit at 6 month. The usual care (waiting list) group will receive educational booklets about a healthy lifestyle. They will be asked to continue to wear the wearable device to monitor PA for 3 months. Participants will then receive the iHBE program after the conclusion of the 12-week program.

5. Inclusion/Exclusion Criteria

Inclusion criteria are (1) participants diagnosed with solid tumor cancer who have completed cancer treatment at least 6 months; (2) diagnosed with diabetes and/or hypertension for at least a year; (3) aged 21 years or older, (4) have an annual household incomes of below \$30,000 for families of three, (5) the average fatigue level within the past 7 days at the level of 3 or more on the 0 (no fatigue) to 10 (worse fatigue) Likert scale and (6) give informed consent.

Exclusion criteria are those (1) currently undergoing treatment for cancer; (2) have an active infection (e.g., fever, localized redness, swelling, sinus congestion); and/or (3) diagnosed with a psychological disorder (e.g., suicidal or homicidal tendencies, extreme anxiety or depression).

6. Drugs/Substances/Devices

None

7. Study Statistics

Phase 2 Data analysis

To test **Hypothesis 2 (Aim 2)** examining the effectiveness of iHBE program on fatigue, pain, well-being, resilience and BDNF levels, generalized estimating equations (GEE) will be used. The models will include time as a within-subject fixed effect (baseline, 3 months, 6 months), group (intervention vs usual care) as a fixed-effect between-subject factor and the group by time interaction. Baseline age, race gender, and BMI will be included as covariates. A significant group by time interaction would signify that the change over time in the outcomes differed for the intervention and usual care groups. GEE was selected because it uses all available data and does not require complete data across time for a participant to be included in the analyses. Correlation will be used to test the relationship between the changes in serum and sweat BDNF levels (**Aim 3**). Change from baseline to 3 months and change from baseline to 6 months will be computed for serum BDNF and separately for sweat BDNF. The correlation between the change scores measured by the different modes will be estimated at each time point

8. Risks: Same as phase 1

9. Benefits: Same as phase 1

10. Payment and Remuneration

Date: November 14, 2018

Principal Investigator: [name]

Application Number: IRB00175781

Phase 2 (Aim 2 and 3) - The participants in both the intervention group and the control group will each receive a total of \$80 (\$20 at the start of the intervention, \$30 at the end of the intervention and \$30 at 6 months)

11. Costs

There will be no cost for participants to participate in this study.

12. Data Safety Monitoring Plan

The PI will review reports reflecting data quality, safety, and monitor for potential adverse events and protocol adherence. The project coordinator, study staffs will meet with the PI weekly to review the progress of the study. The members of the investigative team and scientific advisors will meet monthly to support the study. A Safety Monitoring Committee (SMC) will be formed, consisting of Johns Hopkins University clinician faculty members who are independent of this proposed feasibility study. The SMC will be responsible for overall monitoring of the safety of participants in this proposed study and overseeing the PI, Co-Is, and research assistant.

The PI will be responsible for managing all data, securing privacy and confidentiality, minimizing and identifying risks, monitoring and reporting adverse events or any safety issues, and complying with timely reporting requirements to all applicable regulatory bodies for any adverse events or unexpected problems. Monthly reports will be completed by the PI detailing participant demographics, recruitment status, treatment retention rates, protocol compliance, data gathered and accuracy, and quality assurance or regulatory issues that transpired, and summary of any adverse events. The research team (PI, Co-Is, and research assistant) will meet weekly via face to face or conference calling to discuss data and safety monitoring.

The SMC will meet annually (or more frequently if needed) and review the annual reports completed by the PI; review study safety, integrity, and progress including any adverse events; provide advice in relation to continuing, changing, or terminating the study when necessary; require more frequent reporting as needed; audit the study for compliance and verify authenticity of data; and assess that the research team is complying with informed consenting and other required regulations. These annual meetings will be conducted face-to-face or through conference calls.

The PI, in consultation with the SMC, will provide reports at intervals as required by National Institute of Health and/or other regulatory bodies as well as provide immediate reports as required regarding any adverse or unanticipated problems that may occur.

References

American Cancer Society. (2017). Cancer Facts & Figures 2017. Retrieved September 20, 2017, from <https://www.cancer.org/content/dam/cancer-org/research/cancer-facts-and-statistics/annual-cancer-facts-and-figures/2017/cancer-facts-and-figures-2017.pdf>

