The aim of this phase (specific aim 1) is to obtain participants' perception and acceptability of the program. The number of eligible participants and recruited participants, the number of participants completing the intervention program, and the number of drop out participants will be recorded. The program will be adjusted based on the participant feedback and will be pilot tested in phase 2. We are submitting this application for phase one at this time and will submit phase 2 in the further study action.

Sample and Setting:

The study participants will be recruited from the home health care agencies in Baltimore, Maryland, Johns Hopkins Comprehensive Cancer Center and Johns Hopkins Hospital.

Inclusion criteria are (1) participants diagnosed with solid tumor cancer who have completed cancer treatment at least 6 months; (2) diagnosed with diabetes and/or hypertension for at least a year; (3) aged 21 years or older, (4) have an annual household incomes of below \$30,000 for families of three, (5) the average fatigue level within the past 7 days at the level of 3 or more on the 0 (no fatigue) to 10 (worse fatigue) Likert scale and (6) give informed consent.

Exclusion criteria are those (1) currently undergoing treatment for cancer; (2) have an active infection (e.g., fever, localized redness, swelling, sinus congestion); and/or (3) diagnosed with a psychological disorder (e.g., suicidal or homicidal tendencies, extreme anxiety or depression).

Data Collection Schedule and Procedures. Upon receiving approval from the Johns Hopkins University Institutional Review Board, the study flyer will be posted and distributed at the home health care agencies in Baltimore, Maryland, Johns Hopkins Comprehensive Cancer Center and Johns Hopkins Hospital.

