4 home visits (Week 1-4)	
A research team member will visit participants' home and evaluate exercise problems. The research team will review the physical performance with the participants and help them identify problems and solutions. During these visits, the research team will tailor the exercise to be suitable for the participants' conditions and situation. Participants will practice their exercise with the research team for 15-20 min. The information on home safety will be provided to the participants and their caregivers.

Completion session (end of week 4)	
A research team member will visit participants' home and evaluate the participants' perception and satisfaction for the program using a quantitative semi-structured interview. Participants will be asked to complete the questionnaires. Participants' blood and sweat will be collected.

Table 1: iHBE program activities

Program fidelity: To maintain fidelity of the program, two research assistants/research nurse will receive 1-month project specific training on intervention design, all four exercise options and project implementation. Nurse researchers will receive additional training on how to demonstrate the use of technologies (a wearable device: FitBit Charge 2) and a smartphone application (mEMA) and how to conduct a physical function assessment set PA goals and identify problems and solutions. The nurse researchers will conduct a home visit and follow up phone call under the supervision of a registered nurse. The principal investigator will randomly check home visit and follow up phone call sessions and provide timely feedback. The investigator team will work with the nurse researchers and clinical settings for quality assurance and address any issues that may occur during the study.

Variables and measurements.

Physical function: To ensure participants' safety during home exercise and provide the best recommendation for the type of exercise, the physical function will be measured by asking the participants' perception on their ability to complete a walk for 6 minutes with the perceived exertion level of 3 or below.

The study variables will be measured as follows:

Measure	Description	Psychometrics
NINR Common Data Elements (CDEs)	23-item; measure demographic and disease information data	

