We will explore measurement of variables, exercise choices and tracking mechanisms with participants regarding feasibility and acceptability. The principal investigator will conduct a qualitative semi-structured interview, record and take notes of the interview and discussed participants' feedback with the research teams. The exercise plan, wearable device, and phone application feature will be discussed until consensus program for each option is made.

Table : Data collection process

Task	home visit Baseline: Assessment Week 0	iBHE program				Post intervention Home visit	
		Home visits week					
		1	2	3	4		
Assessment: perception, goal, FTSST, and 6MWT	X						
Demographic and disease information questionnaire	X						
PROMIS fatigue and PROMIS pain	X					X	
Short form survey (SF-36)	X					X	
Connor-Davidson Resilience Scale	X					X	
Physical activity (steps) and HR (from wearable device)*	X	X	X	X	X	X	
Blood sample for BDNF level	X					X	
Sweat sample for BDNF level	X					X	

*objective physical activity will be measured daily

Date: November 14, 2018

Principal Investigator: [name]

Application Number: IRB00175781

5. Inclusion/Exclusion Criteria

Inclusion criteria are (1) participants diagnosed with solid tumor cancer who have completed cancer treatment at least 6 months; (2) diagnosed with diabetes and/or hypertension for at least a year; (3) aged 21 years or older, (4) have an annual household incomes of below \$30,000 for families of three, (5) the average fatigue level within the past 7 days at the level of 3 or more on the 0 (no fatigue) to 10 (worse fatigue) Likert scale and (6) give informed consent.

Exclusion criteria are those (1) currently undergoing treatment for cancer; (2) have an active infection (e.g., fever, localized redness, swelling, sinus congestion); and/or (3) diagnosed with a psychological disorder (e.g., suicidal or homicidal tendencies, extreme anxiety or depression).

6. Drugs/ Substances/ Devices

None

7. Study Statistics

Data analysis:

Phase 1:

Aim 1: Examine the feasibility and acceptability of the iBHE program among low-income cancer survivors living with co-morbid conditions.

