Primary objectives of this phase are to evaluate the feasibility and acceptability of the iBHE program. Eight participants who have completed treatment for a solid tumor cancer with at least one comorbidity (e.g., diabetes and/or hypertension) will be assigned to an open-label trial of the iBHE. At the completion of the program (4 weeks), the primary investigator will conduct a semi-structured interview to gather feedback on the program feasibility, goal setting, problem-solving strategies, exercise choices and tracking mechanisms, program feasibility, and acceptability. The interview will be recorded and transcribed verbatim.

The feasibility of the program

The feasibility of the intervention program will be determined from the achievement of individual physical activity goal. At the end of 4 week program, research team will review the participants ability to achieve at least 75% of the individual's exercise goal (for example, if the goal is to exercise at the fat burn level (50-60% maximum heart rate measured by FitBit) for 30 min/day 3 days week, participants can exercise for 30 min for at least 2 days or FitBit data showed more than 60 active min). For this first phase, at least 50% of participants will need to meet 75% of personal goal in at least 2 weeks for the trial to continue onto phase II. For participants who do not achieve 75% of their individual exercise goal, the barriers will be identified that the weekly goals will be revised until the 75% of weekly personal exercise goals is met. If the feasibility threshold (less than 50% of participants achieve 75% of their weekly goals for 2 weeks) does not reach, we will adjust the goal setting process and recruit more participants.

The feasibility of the recruitment will be determined by the number of screened participants, eligible participants and participants who refuse to be in the study and rational will be examined and recorded as indicator of feasibility. The feasibility of delivering the program will be evaluated by examining the number and timing for actual versus planned home visit and the duration of each visit. The intervention checklist will be filled by the research assistants for each home visit to assess the intervention content delivery.

The acceptability of the program

The acceptability of the program will be assessed using the semi-structure interview. The common feedback and suggestion for intervention during the semi-structure interview will be noted.

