Date: November 14, 2018

Principal Investigator: [name]

Application Number: IRB00175781

The compliance of the program

The compliance of this program will be monitored using active min and daily heart rate zone data from the wearable device (FitBit Charge 2). The weekly goals on number of day for physical activity and duration of the physical activity will be set. The number active min and duration of the heart rate in at least “Fat Burn” zone per day will be recorded for the duration of physical activity/day. The number of days the participant achieve the goals (duration and days) for physical activity will be used to measure the compliance of the program.

The descriptive information from the phase I to help inform alternative approaches to the anticipated analysis, sample size estimates for phase II, and additional key variables to be measured in phase II (intervention dose, fidelity, and additional process variables).

The program modification

Prior to phase 2, the primary investigator will discuss participants' feedback with the research teams.

The modification of exercise plan, wearable device, and phone application feature will be discussed until consensus program for each option is made.

8. Risks

Potential Risks:

The risks of participating in this study are minimal. Potential risks include

1. complications during the blood drawing for examples pain and bleeding at the drawing site.
2. complications during the sweat collection for examples rash, itching, redness and swollen.
3. minimum discomfort might occur during the wearable device (worn like a bracelet).
4. complications (e.g., fainting, injury) during the exercise program.

During the proposed study, if there is a serious adverse event, anticipated to be an uncommon occurrence, the PI will unmask treatment group assignment when necessary for the safety of the participant. The administration of the intervention may be discontinued at the participant's request or by the investigator, based on clinical judgment. Participants will be instructed to report any adverse event experienced after treatment without delay.

Adequacy of Protection against Risks: The safety of the study participants is essential. The primary investigator and research team will take all precautions to protect the participants against risks.

Protection against Risks: The principal investigator (PI) and research team plan to prevent the following risks:

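### Phase 1 acceptability is measured only by an interview at programme completion, so participants who stop early contribute no interview and no recorded reason for stopping

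*Combined protocol and SAP*

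**What the plan says.** Section 7 (Study Statistics, Phase 1, Aim 1) makes feasibility and acceptability the primary objectives of an open-label phase with eight people: "Eight participants who have completed treatment for a solid tumor cancer with at least one comorbidity". Its paragraph on acceptability names the semi-structured interview and no other measure. The interview is timed in the same section: "At the completion of the program (4 weeks), the primary investigator will conduct a semi-structured interview". The Phase 1 procedures in Section 4 and the completion row of Table 1 place it at the same point.

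On people who leave, Section 4 says only that "the number of drop out participants will be recorded", alongside the number who complete. Section 7 asks for the reasons of those who decline to enter the study; nothing asks for the reasons of those who stop. Section 10 ties the Phase 1 payment of $40 to the baseline data and the interview. The programme-modification paragraph of Section 7 then uses participants' feedback to settle the changes made before Phase 2.

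Exercise goals are handled differently. The formal review is at the end: "At the end of 4 week program, research team will review the participants ability to achieve at least 75% of the individual's exercise goal". The rule for moving on to the randomised phase reads: "at least 50% of participants will need to meet 75% of personal goal in at least 2 weeks for the trial to continue onto phase". The data behind it are gathered throughout. The footnote to the data collection table says "objective physical activity will be measured daily", and Table 1 says of the visits in weeks 1 to 4: "The research team will review the physical performance with the participants and help them identify problems and solutions".

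**The concern.** Phase 1 exists to learn whether low-income survivors with comorbidity can and will do the programme, and to repair it before randomisation. People who give up in week 1 or 2 hold some of the most direct evidence of what does not work. The only instrument for acceptability is applied at a visit that they will not reach, and the plan provides no other occasion, and no payment, for hearing from them. If those who stop think less well of the programme than those who finish, the acceptability findings lean upwards and the redesign misses the problems that made people leave. If they stop for unrelated reasons, there may be no lean at all, but without recorded reasons the team cannot tell the two situations apart.

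**Working it through.** **1. Which assessments depend on reaching the end of week 4**

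| Element | Source of data | Needs the participant at completion? |
|---|---|---|
| Acceptability | Semi-structured interview (Section 7; Section 4; Table 1) | Yes |
| Goal achievement | Wearable data, daily; performance reviewed at weekly visits (data collection table; Section 7, compliance; Table 1) | No |
| Drop-out | Count (Section 4) | No, but gives no reasons |

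Only acceptability is lost when a participant stops.

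**2. Size for acceptability**

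With k of 8 stopping early, the share of interviews lost is k/8: 12.5%, 25% and 37.5% for k = 1, 2 and 3.

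The plan sets no acceptability score, so any bias figure is only an illustration. Suppose s of the 8 − k finishers are favourable and no leaver is. The summary shows s/(8 − k) where all eight would give s/8. The gap is s·k/[8(8 − k)], which is largest when every finisher is favourable and then equals k/8. For k = 2 that is 6/6 = 100% against 6/8 = 75%. If leavers think as finishers do, the gap is zero.

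The documents give no Phase 1 drop-out rate. The only attrition figure is 12%, in the Phase 2 sample size justification (25 falling to 22 per group), for a longer study. With independent drop-out at rate d, P(at least 1) = 1 − (1 − d)^8 and P(at least 2) = 1 − (1 − d)^8 − 8d(1 − d)^7.

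| Assumed d | At least 1 of 8 | At least 2 of 8 |
|---|---|---|
| 6% (half the Phase 2 figure) | 1 − 0.610 = 39% | 1 − 0.610 − 0.311 = 8% |
| 12% (Phase 2 figure) | 1 − 0.360 = 64% | 1 − 0.360 − 0.392 = 25% |
| 25% | 1 − 0.100 = 90% | 1 − 0.100 − 0.267 = 63% |

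**3. The 50% continuation rule**

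No calculation accompanies the rule, so there is no stated figure to reproduce. The achievers needed are half the denominator, rounded up.

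| Drop-outs | Needed, all 8 counted | Needed, completers only | Completers-only number as share of 8 |
|---|---|---|---|
| 0 | 4 of 8 | 4 of 8 | 50% |
| 1 | 4 of 8 | 4 of 7 | 50% |
| 2 | 4 of 8 | 3 of 6 | 37.5% |
| 3 | 4 of 8 | 3 of 5 | 37.5% |
| 4 | 4 of 8 | 2 of 4 | 25% |

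With none or one stopping, the denominator makes no difference. With two or three, the decision differs only if exactly three people achieve: 3/6 = 50% or 3/5 = 60% passes, and 3/8 = 37.5% does not.

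Assume that leavers do not achieve and that each completer achieves with probability 0.5. The exact binomial chance of passing, all eight against completers only, is 0.344 against 0.656 with two drop-outs and 0.188 against 0.500 with three. At 0.4 the pairs are 0.179 against 0.456 and 0.087 against 0.317. Averaged over a 12% drop-out rate, the gap is much smaller: 0.500 against 0.580 at 0.5, and 0.298 against 0.366 at 0.4.

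**The case against.** The plan does listen to participants before week 4. At each weekly home visit the team looks at exercise problems and helps to solve them, and Section 7 has barriers identified for anyone who misses a goal. A person who stops in week 3 may already have said what was wrong. Section 7 also compares actual with planned visits, and the monthly reports in Section 12 include retention, so attrition would be visible. Finishing is not the same as liking the programme, and finishers can be critical. All of this stands, which is why the findings rest mainly, not wholly, on finishers. But the visits are coaching sessions, not an assessment of acceptability. They end when the person stops, and retention figures do not say why anyone left.

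A reader might go further and infer that goal achievement, too, is assessed only at the week-4 visit, so that leavers escape the continuation rule and the programme looks more feasible than it is. The documents do not support that. Activity is recorded daily and performance reviewed weekly, and the end-of-programme step is a review by the team that does not call for attendance. The rule needs only two successful weeks, so someone who stops after week 2 or 3 can be judged on existing data, and someone who stops sooner has not met it. The rule speaks of participants without restriction, and the plain reading is all eight; Section 4 uses a separate phrase when it means completers.

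**Conclusion.** The gap is real and confined to acceptability. As written, a participant who stops early supplies no acceptability interview and no recorded reason for stopping, although acceptability is a primary objective and the feedback shapes the Phase 2 programme. The loss is 12.5% of the interviews per leaver. Upward bias is possible but not established: it requires that leavers hold less favourable views, and its size depends on a Phase 1 drop-out rate that the documents do not give.

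The continuation rule needs only a clarifying sentence. A changed decision would require a completers-only denominator, which the text does not state, together with at least two drop-outs among eight and a particular number of achievers. Nor would missing the threshold simply end the trial: Section 7 says that the team would then adjust goal setting and recruit more participants.

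**What to change.** In Sections 4 and 7 for Phase 1, add that any participant who stops early is offered the same semi-structured interview, by telephone if needed and with the same payment, and that the reason for stopping is recorded. In the acceptability summary, identify which feedback came from people who stopped; with eight participants a label on each item is enough.

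As a clarification, state that the 50% rule counts everyone who started, with early leavers judged on the weeks of wearable data they have and otherwise counted as not achieving.

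The cost is a few sentences of protocol text and a few extra calls by existing staff. Some people who stop will decline, so the gap will narrow but may not close; the number who decline should be reported.
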